10.3.3. Secondary Endpoints for Efficacy

For each of the continuous secondary endpoints, the actual value, change from baseline and percentage change from baseline for all secondary endpoints will be summarized by visit and treatment group using the n, mean, SD, median, first and third quartiles, minimum, and maximum values. The comparison of the active arms (separately) will be performed using a Mixed Model for Repeated Measures (MMRM)/ Analysis of Covariance model with treatment, Visit, and baseline value in the model. The least square means of the treatment difference, standard errors, 95% CI and p-value for the treatment will be presented at each visit. A 2-sided alpha of 0.05 will be used to determine statistical significance for Treatment. If deemed appropriate, the two active arms may be combined to evaluate any treatment effect for the changes from the baseline.

For categorical secondary endpoints, the number of participants who meet the endpoint and the percentage will be summarized. The percentage will be calculated using those participants who had a value at the time point. Statistical testing may be performed between the two treatments using a Fishers Exact Test. If deemed appropriate, the two active arms may be combined to evaluate any treatment effect for the shift from the baseline.

The analyses of the secondary endpoints will be performed on ITT based on all available data, without using any imputation method for missing data.

10.3.4. Safety Analyses

Safety will be evaluated by assessment of clinical laboratory tests, physical examinations, vital signs measurements, and ECG readings at various time points during the study, and by the documentation of AEs.

AE verbatim text will be coded and classified by body system and preferred (coded) term using the MedDRA. All AEs, both serious and non-serious will be listed. AE summaries by study part and treatment group, of the number and percent of participants reporting each event at least once will be generated.

Clinical chemistry, hematology, and urinalysis values will be listed for each participant and flagged high or low relative to the normal range where appropriate. Descriptive summary statistics will be created by study part, treatment and assessment time.

Other safety data will be summarized descriptively by treatment and time on the Safety Population. Details will be provided in the SAP.

10.3.5. Pharmacokinetic Analyses

Serum compound concentration-time data will be analyzed by non-compartmental methods with Phoenix WinNonlin or other PK software programs. Calculations will be based on the actual sampling times recorded during the study for the PK Population. From the plasma concentration-time data, C_{trough} will be determined:

Additional PK parameters may be calculated. PK data will be presented in graphical and tabular form and will be summarized descriptively by Treatment.

10.3.6. Pharmacodynamic Analyses

All participants in the ITT population will be included in the summaries of PD data. The actual value, change from baseline and percentage change from baseline for all PD parameters will be summarized by visit and treatment group using the n, mean, SD, median, first and third quartiles, minimum, and maximum values. Statistical testing may be performed between the two treatment groups using mixed models. Details will be provided in the Statistical Analysis Plan.

Serum IgG and IgG subclass (1-4) levels will be summarized as both raw values as well as percent change from baseline (intra-participant assessment). Additional PK/PD and PD/PD relationships may be evaluated. PD data will be presented in graphical and tabular form and will be summarized descriptively. The correlation coefficients will be generated between PK/PD parameters.

10.3.7. Other Analyses

The analysis of the exploratory endpoints will include all participants in the ITT population.

11. ADVERSE EVENTS (AE) AND SERIOUS ADVERSE EVENTS (SAES)

The Principal Investigator or site staff is responsible for detecting, documenting and reporting events that meet the definition of an AE or SAE. All SAEs must be reported to the Sponsor within 24 hours of awareness of the event (Section 11.3).

Once study participants have completed the study, the Principal Investigator is not obligated to actively seek AEs or SAEs. However, if the Principal Investigator learns of any SAE, including a death, at any time after a participant has been discharged from the study, and he/she considers the event reasonably related to the investigational product or study participation, the Principal Investigator must notify the Sponsor at [REDACTED] within 24 hours of awareness.

11.1. Definition of Adverse Events

An AE is any untoward medical occurrence in a participant or clinical investigation participant, temporally associated with the use of a medicinal product, whether or not considered related to the medicinal product.

An AE can therefore be any unfavorable and unintended sign (including an abnormal laboratory finding), symptom, or disease (new or exacerbated) temporally associated with the use of a medicinal product.

Events meeting the definition of an AE **include but are not limited to:**

- Any clinically significant, new or worsened, abnormal laboratory test results (hematology, clinical chemistry, or urinalysis) or other safety assessments (e.g., ECGs, radiological scans, vital signs measurements). Clinical significance is determined based on the medical and scientific judgement of the Investigator.
- Signs, symptoms, or the clinical sequelae of a suspected interaction (e.g. with medications or food).
- Signs, symptoms, or the clinical sequelae of an overdose of either investigational product or a concomitant medication (overdose without an AE should be reported as a protocol deviation).

Events that **do not** meet the definition of an AE include:

- Anticipated day-to-day fluctuations of pre-existing condition(s), including the disease under study.
- Abnormal or worsening laboratory, imaging, or other safety findings that are not clinically significant.
- Medical or surgical procedures (e.g., endoscopy, appendectomy); the condition that leads to the procedure is an AE.
- Situations where an untoward medical occurrence did not occur (social and/or convenience admission to a hospital).

11.2. Definition and Reporting of Serious Adverse Events

Serious adverse events must be entered within 24 hours of awareness and marked as a SAE within the AE eCRF form, which will send an immediate auto notification to [REDACTED] and the Medical Monitor.

If the eCRF is not available, the site must email [REDACTED] and the Medical Monitor within 24 hours of the study site personnel's knowledge of the event.

A SAE is any untoward medical occurrence that, at any dose:

- Results in death
- Is life-threatening

The term 'life-threatening' in the definition of 'serious' refers to an event in which the participant was at immediate risk of death at the time of the event. It does not refer to an event, which hypothetically might have caused death, if it were more severe.

- Requires hospitalization or prolongation of existing hospitalization

Hospitalization planned prior to signing the informed consent is not considered an SAE. Surgeries and other interventions that were under consideration prior to signing the informed consent are not considered an SAE if the underlying condition has not changed from baseline.

“Hospitalization” includes admission to the hospital of any duration. It does not include emergency room visits. Complications that occur during hospitalization are AEs and are SAEs if they prolong hospitalization or fulfill any other serious criteria.

Hospitalization for elective treatment of a pre-existing condition that did not worsen from baseline is not considered an AE.

- Results in disability/incapacity

The term disability means a substantial disruption of a person’s ability to conduct normal life functions. This definition is not intended to include experiences of relatively minor medical significance such as uncomplicated headache, nausea, vomiting, diarrhea, influenza, and accidental trauma (e.g. sprained ankle) which may interfere or prevent everyday life functions but do not constitute a substantial disruption.

- Is a congenital anomaly/birth defect
- Is an important medical event that may jeopardize the participant or may require medical or surgical intervention to prevent one of the other outcomes listed in the above definition. Examples of such events are allergic bronchospasm, blood dyscrasias or convulsions where treatment prevents the need for hospitalization.

The following should always be considered serious: invasive or malignant cancers, and development of drug dependency or drug abuse.

- Deaths considered to be the result of progression of WAIHA or failure of treatment should be recorded as SAEs; the most prominent event (e.g. autoimmune hemolytic anemia or thrombosis due to WAIHA) should be recorded as the event term with an outcome of death.
- Hospitalization for urgent transfusion or treatment of symptoms associated with recurrence of WAIHA; the most prominent event should be recorded as the event term.

11.3. Time Period and Frequency for Collecting AE and SAE Information

- AEs will be collected from the time of informed consent through the follow-up period, at the timepoints specified in the Section 8.1, Time and Events Table.
- Medical occurrences that begin prior to any study procedure but after obtaining informed consent may be recorded on the Medical History/Current Medical Conditions section of the eCRF.
- All SAEs will be recorded and reported to the Sponsor within 24 hours of site awareness.
- Any SAEs assessed as related to study participation (e.g., protocol-mandated procedures, invasive tests, or change in existing therapy) or related to investigational product will be recorded from the time a participant consents to participate in the study up to and including any follow-up contact.

11.4. Method of Detecting and Reporting AEs and SAEs

Care will be taken not to introduce bias when detecting AEs and/or SAEs. Open-ended and non-leading verbal questioning of the participant is the preferred method to inquire about AE occurrence. Appropriate questions include:

- “How are you feeling?”
- “Have you had any (other) medical problems since your last visit/contact?”
- “Have you taken any new medicines, other than those provided in this study, since your last visit/contact?”

All AEs and SAEs should be promptly recorded in the eCRF, completing all fields for which data is available. When known, the diagnosis should be entered as the event term in the eCRF, rather than individual symptoms. When the diagnosis is unclear, key symptoms may be entered, and the investigator should obtain appropriate tests to establish a diagnosis, if possible. After the diagnosis is determined, individual symptoms of that diagnosis may be removed from the database. All relevant seriousness criteria should be entered for each SAE. Discharge summaries should be requested for all hospitalizations.

For SAEs, the eCRF will send an auto notification to [REDACTED] and the Medical Monitor when the form is saved. Each SAE should be assigned a causality at the time of entry, as this is required to determine regulatory reporting. Follow-up information regarding the SAE, including hospital discharge summary, should be emailed to [REDACTED] after redacting all personally identifying information regarding patient or hospital staff (per European Global Data Protection Regulation).

11.5. Assessing Severity of AEs and SAEs

Severity describes the intensity of a specific event (as in mild, moderate, or severe myocardial infarction); the event itself, however, may be of relatively minor medical significance, such as a severe headache. This is not the same as “serious,” which is based on participant/event outcome or action taken.

The Investigator must determine the severity of each AE according to the following criteria:

Criteria for Determining the Grade/Severity of Adverse Event Terms

Grade	Criteria
1/Mild	Asymptomatic or mild symptoms, clinical or diagnostic observations only; intervention not indicated
2/Moderate	Minimal, local, or noninvasive intervention indicated; limiting age-appropriate instrumental activities of daily living
3/Severe or medically	Not immediately life-threatening; hospitalization or

significant	prolongation of hospitalization indicated; disabling; limiting self-care activities of daily living
4/Life-threatening	Life threatening consequences; urgent intervention indicated. (Note that the seriousness criteria “life-threatening” applies only if the event is immediately life-threatening; an event such as cancer or neutropenia may be Grade 4 but not meet seriousness criteria of Life-threatening)
5/Death	Death related to adverse event

Adverse event severity should be recorded in the appropriate section of the AE eCRF and in the participant’s source documents.

11.6. Assessing Causality of AEs and SAEs

Regulatory authorities require that both investigator and sponsor assess whether there is a reasonable possibility that the study treatment caused each AE. This assessment requires careful medical consideration of each event in relationship to the timing of drug administration, the presence of other factors which may have caused the event (underlying illness, concomitant medication, complications, exposure to other toxins or allergens, environmental factors, etc.), and the effects of stopping and/or restarting the study treatment. The following definitions are to be used for the relationship of the AE to Study Treatment:

The investigator will assess the causality of each reported AE as follows:

- Probably related: an AE occurring at a reasonable time following administration of a drug, where other causes are unlikely, there is evidence to suggest that the drug caused the event, and/or where the event recurs after reintroduction of the drug (without other explanation for the recurrence).
- Possibly related: an AE occurring at a reasonable time following administration of a drug and for which there is a reasonable possibility that the drug caused the event, e.g. there is some evidence to suggest a causal relationship.
- Not related: an AE with poor or no relationship to the timing of drug administration, or where another cause such as underlying disease, complications, or other medications reasonably explains the event, or where the event does not recur after continued administration or reintroduction of the drug for an adequate period.

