3.3.3.1. Safety

See Investigator's Brochure for details.

[figure not shown]
RVT-1401 has been well tolerated with no Grade 3 or 4 adverse events (AEs), and no withdrawals due to AEs. There have been two serious adverse events (SAEs) (Malpighian carcinoma in left side of the neck and appendicitis) considered unrelated to study drug.

All other AEs in subjects receiving RVT-1401 have been reported as mild or moderate.

The most frequently reported AE was injection site reactions (erythema and/or swelling). The rate of injection site reactions was similar between RVT-1401-treated and placebo-treated subjects and was not dose-related. Injection site reactions have generally resolved within a few hours after dosing; there were two exceptions of mild swelling (one RVT-1401- and one placebo-treated subject) that resolved after 3 and 4 days, respectively. Additionally, injection site reactions were not consistently observed following every injection in the repeat dose cohorts.

Preliminary data suggest no subject who has received RVT-1401 had clinically relevant changes in vital signs or laboratory results, or on electrocardiogram (ECG).

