### 9.1 Adverse Events

The adverse events (AEs) will be coded by the Medical Dictionary for Drug Regulatory Activities (MedDRA) version 22.1 or higher. A treatment-emergent adverse event (TEAE) is defined as any AE onset post first treatment. A listing of all subjects reporting TEAEs will be presented. A separate listing of serious TEAEs will be provided. A by-subject listing containing the AEs by the MedDRA system organ class and preferred term will be created. This listing will include start and end dates of the event, severity, and relationship to study drug. Injection site reactions will also be presented in a separate listing.

The AE data will not be imputed other than a missing date.

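### Protocol 11.6 lets non-recurrence on further dosing make an adverse event *Not related* on its own, even when timing fits and no other cause is found

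*Protocol*

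**What the plan says.** Protocol 11.6 opens with the standard to be applied: "Regulatory authorities require that both investigator and sponsor assess whether there is a reasonable possibility that the study treatment caused each AE". It asks for medical judgement that weighs the timing of dosing, other factors that could have produced the event, and what happened when treatment was stopped or restarted. Three categories follow.

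- *Possibly related* covers an event at a reasonable time after dosing "for which there is a reasonable possibility that the drug caused the event".
- *Not related* has three alternatives. The first is "an AE with poor or no relationship to the timing of drug administration". The second is "or where another cause such as underlying disease, complications, or other medications reasonably explains the event". The third is "or where the event does not recur after continued administration or reintroduction of the drug for an adequate period".

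The length of event-free dosing that the third alternative needs is not defined, and no rule covers an event that fits two categories.

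The label is used in two places. Protocol 11.4 says: "Each SAE should be assigned a causality at the time of entry, as this is required to determine regulatory reporting". SAP 9.1 plans a by-subject adverse event listing and says of it: "This listing will include start and end dates of the event, severity, and relationship to study drug".

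**The concern.** Many drug effects do not repeat with each dose. They can be self-limiting, confined to early doses, or intermittent. The absence of a second episode is therefore weak evidence that the drug did not cause the first. The third alternative treats it as conclusive and asks for neither poor timing nor a competing cause.

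Two things are at stake. The first is consistency: two investigators could code the same event differently and both comply with 11.6. The second is direction: the clause can only move events towards *Not related*. Safety and tolerability is a primary endpoint (Protocol 4, SAP 2.2.1). SAP version 3.0 reduces the Cohort 1 output to listings for five participants, so each relationship entry will be read individually, with no aggregate analysis beside it.

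**Working it through.** The plan states no figure on this point, so the check is one of logic and reach.

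**Step 1. The definition as a rule.** Let A be poor timing, B another cause that reasonably explains the event, and C no recurrence on continued or resumed dosing. As written, *Not related* = A or B or C. *Possibly related* needs reasonable timing (so A is false) and a reasonable possibility of drug causation.

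| Case | A | B | C | *Not related* as written | *Possibly related* |
|---|---|---|---|---|---|
| 1. Timing fits, no other cause, event recurs | no | no | no | no | can be met |
| 2. Timing fits, no other cause, no recurrence | no | no | yes | **yes, by C alone** | can be met |
| 3. Timing fits, another cause explains it | no | yes | either | yes, by B | a matter of judgement |
| 4. Poor timing | yes | either | either | yes, by A | not met |

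Case 2 is the fault. It meets two categories with opposite meanings, and only the non-recurrence clause brings it into *Not related*.

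**Step 2. Against the section's own standard.** The opening of 11.6 treats the effect of stopping or restarting as one factor among several. The third alternative turns that factor into an exclusion. It also extends it to dosing that was never interrupted, which the opening does not list.

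**Step 3. An illustration from the protocol.** Protocol 6.8.3 says RVT-1401 is expected to lower albumin, and it describes interruption followed by restart in some participants. Suppose a fall is recorded as an adverse event, dosing resumes and the fall does not return. The third alternative then supports *Not related* for an effect that the protocol attributes to the drug.

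**Step 4. Where C can operate.** It needs further dosing after the event.

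| Situation | Source | Can C apply? |
|---|---|---|
| Grade 1–2 event, weekly dosing continues | Protocol 5.1, 6.9.1 | Yes |
| Grade 3 event not attributed to WAIHA | Protocol 6.9.1: drug withheld, restart only after discussion with the medical monitor | Only after a restart |
| Grade 4 toxicity other than hemoglobin decrease | Protocol 6.9.1: permanent discontinuation | No |
| Serious infection or anaphylaxis | Protocol 6.8.4: stopping criteria | No, once dosing stops |
| Any SAE at first entry | Protocol 11.2 and 11.4: entry within 24 hours of awareness, causality assigned then | Usually not, because the next dose is typically still to come |

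For SAEs this leaves three routes: late awareness, later revision of the causality entry, and restart after a grade 3 event.

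**Step 5. What happens to a mislabelled event.** Protocol 11.3 sends every SAE to the sponsor within 24 hours of site awareness, whatever the causality. SAP 9.1 lists all treatment-emergent events, lists serious ones separately, and plans no table restricted to related events. The event stays visible with its dates and severity. Only its relationship entry is wrong.

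**The case against.** The strongest reply is that 11.6 calls for careful medical judgement and is not an algorithm. The sponsor also assesses causality, and a sensible investigator would not dismiss a well-timed event merely because it did not return. Much of this stands as mitigation. It does not remove the fault: the text tells assessors to use these definitions, gives the sponsor no separate scale, and has no rule for disagreement between investigator and sponsor.

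A reader might infer three stronger claims, none of which the documents support.

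- **That SAEs drop out of reporting or that SUSARs are lost.** Steps 4 and 5 show why this goes too far. Causality is assigned at entry, dosing stops after many serious events, and every SAE reaches the sponsor. A single serious infection while IgG is suppressed is a poor example, because an infection needing hospitalization or intravenous antibiotics is itself a stopping criterion.
- **That the Phase 1 experience proves non-recurrence invalid as a test for this drug.** Protocol 3.3.3.1 does report that "injection site reactions were not consistently observed following every injection in the repeat dose cohorts". It also says that the rate of these reactions was similar on placebo and not dose-related. The passage shows that a reaction to an injection need not repeat. It does not show an intermittent effect specific to RVT-1401.
- **That most drug-caused events would be mislabelled.** One can assume a per-dose risk and compute the share of participants with a single episode over 12 doses. Neither document gives such a risk, the length of event-free dosing required is undefined, and constant risk over 12 doses ignores the stopping rules. Such a share would not measure miscoding.

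**Conclusion.** The point holds as a fault in a stated rule. Read as written, non-recurrence alone makes an adverse event *Not related*, against the section's own standard and in unresolved overlap with *Possibly related*.

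Its reach is limited. It bears mainly on non-serious events where dosing continues, and on the relationship entries for the five Cohort 1 participants. The effect on SAE or SUSAR status is indirect and confined to the three routes in Step 4. The number of labels affected cannot be estimated from the documents.

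The conclusion assumes that assessors apply 11.6 as printed and that no eCRF guidance outside these documents already restricts the clause. The correction should be made because it is cheap and the error runs in one direction. It does not call the conduct of the trial into question.

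**What to change.** Replace the definition in Protocol 11.6 with wording such as: *Not related: the timing of the event does not fit drug administration, or another cause reasonably explains it. Absence of recurrence on continued or resumed dosing may support this category but does not by itself establish it.* Then add: *An event with reasonable timing and no other reasonable explanation is not recorded as Not related on non-recurrence alone.* Carry the same text into the eCRF completion guidance.

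This changes case 2 in the table and leaves cases 1, 3 and 4 as they are. A general rule that *Possibly related* prevails whenever two categories are met should not be added. It could also reclassify case 3, where underlying disease or another medication reasonably explains the event.

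For Cohort 1, events already coded *Not related* can be checked for sole reliance on non-recurrence. With five participants this is a small task.

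The cost is two or three sentences in 11.6 and the matching guidance. The downside is that somewhat more events will be recorded as possibly related. No dosing, stopping or rescue provision is affected.
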